2.7.1 Other Secondary and Exploratory endpoints

Disease control rate (DCR)

Disease control rate (DCR) is the proportion of patients with a best overall response of CR, PR, or SD lasting 15 weeks or longer (corresponds to the schedule of the first tumor assessment [16±1 week]). A patient will be considered to have SD for 15 weeks or longer if a SD (or NCR/NPD) response is recorded at 15 weeks or later from randomization. A patient is considered to have PD if the PD occurred at or before week 25, and not qualifying for CR, PR, and SD. The objective of this endpoint is to summarize patients with signs of “activity” defined as either shrinkage of tumor (regardless of duration) or slowing down of tumor growth. DCR will be calculated using the FAS for both central review and investigator tumor assessments.

DCR will also be calculated during the re-treatment period for those that are randomized to the Lutathera arm, and then re-treated with Lutathera. In this case, DCR is the proportion of patients with a best overall response of CR or PR or SD lasting 15 weeks or longer after 1st re-treatment dose of Lutathera, and will be assessed using investigator tumor assessments.

Duration of response

The Duration of Response (DOR), for participants with BOR of unconfirmed CR or unconfirmed PR according to RECIST 1.1, is defined as the time from initially meeting the criteria for response (unconfirmed CR or unconfirmed PR) until the time of progression by RECIST 1.1 or death due to underlying cancer. DOR will be reported descriptively for each group without comparison between groups. The censoring rules in [Table 2.5-1](#) apply. DOR will be calculated using the subset of responders in the FAS for both central review and investigator tumor assessments.

DOR will also be calculated during the re-treatment period for those that are randomized to the Lutathera arm, and then re-treated with Lutathera. In this case, DOR is defined as the time from initially meeting the criteria for response after receiving re-treatment with Lutathera (CR or PR) until the time of progression by RECIST 1.1 (locally assessed) or death due to underlying cancer.

Overall Survival (OS)

The time from the randomization date until the day of death due to any cause will be analysed with three different approaches, that all employ Cox regression to obtain the hazard ratio and its 95% confidence interval.

1. ITT approach, which analyses data with treatment allocated according to randomization

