2. Rank Preserving Structural Failure Time model (RPSFT), which uses an acceleration factor to adjust for any cross-over from Octreotide to Lutathera or for re-treatment of Lutathera for those in the investigational arm; this implies a modification of the

proportional hazards model, see [Section 5.4.1](#). This approach will be analyzed in the final study analysis, and not in the primary PFS analysis.

3. IPCW, which uses Inverse Probability of Censoring Weighting to adjust for any cross-over from Octreotide to Lutathera or for re-treatment of Lutathera for those in the investigational arm, see [Section 5.4.1](#). This approach will be analyzed in the final study analysis, and not in the primary PFS analysis.

ITT approach is primary. Approaches 2 and 3 are outside the scope of the primary analysis, and will be conducted in the final analysis. The analysis proceeds by Cox regression as in the primary analysis of PFS.

Reasons for censoring ('Alive' or 'Lost to follow-up') and death cause will be listed by treatment arm. Survival status, reason for censoring and death cause will be listed. Patients not known to have died will be censored for 'Loss to follow-up' if the time between their last contact date and the analysis cut-off date is longer than 12 months + 2 months window (i.e. the planned interval between two OS follow-up visits in follow up plus the 1-month window on either side).

Time to second progression (PFS2)

As additional exploratory end-point, the Time to Second Progression (PFS2) will be assessed in the two study arms. PFS2 is defined as the time from randomization to the first documented progression after the start of next-line anti-neoplastic therapy or death from any cause, whichever occurs first. The first documented progression on next-line treatment is based on investigator RECIST assessment of PD. It is recognized that the limitation due to potential cross-over or re-treatment and the lower scans frequency during follow-up will reduce the possibility to reach firm conclusions on PFS2.

- Next-line therapy is defined as the first new (systemic) anti-neoplastic therapy initiated after discontinuation of study treatment regardless of the discontinuation reason. Drugs given as part of the same regimen should be considered as one line (i.e., part of the next-line therapy).
- Re-treatment with Lutathera (additional cycles after completion of the 4 cycle treatment on study) will count as next-line anticancer therapy.

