- For estimation without stratification the following applies. An unadjusted Cox model will be used, i.e., the MODEL statement will include the treatment group variable as the only covariate.
- For estimation with stratification the following applies. A stratified unadjusted Cox model will be, i.e., the MODEL statement will include the treatment group variable as the only covariate and the STRATA statement will include stratification variable(s).

Hazard ratio with two-sided 95% confidence interval will be based on Wald test.

Treatment of ties

The STRATA statement in LIFETEST procedure will be used to analyze time to event data with ties. The PHREG procedure in SAS with option TIES=EXACT will be used to fit the Cox proportional hazards model.

Checking proportionality of hazard assumption

Plots (SURVIVAL LOGSURV LOGLOGS) generated by LIFETEST procedure in SAS will be used to provide visual checks of the proportional hazard assumption.

- SURVIVAL plots estimated survivor functions. The shape of the curves should be basically the same if hazards are proportional.
- LOGSURV plots the cumulative hazard functions. The larger cumulative hazard should be a multiple of smaller if hazards are proportional
- LOGLOGS plots log (cumulative hazard). The LOGLOG plot will show parallel curves if hazards are proportional.

As an exploratory measure, to test the proportional hazard assumption, the treatment group * time interaction will be added in the MODEL statement in PHREG procedure in SAS. Evidence that interaction is not zero is evidence against proportional hazards. Further, the correlation between time and Schoenfeld residuals will be calculated to provide further evidence concerning the degree of proportionality.

Multiplicity adjustment

No adjustment for multiplicity will be applied. To protect the type I error for the primary and key secondary endpoints, these will be tested in a hierarchical fashion in the following order: PFS (centrally assessed), ORR, QoL Global Health (TTD), QoL Diarrhea (TTD), fatigue (TTD), and pain (TTD).

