In other words, the drug free survival time is independent of the randomization within the different strata of the baseline risk factor. Therefore, a procedure for estimating the parameter ψ can be based on computing $\hat{U}_i(\psi)$ for various values of ψ and finding a value $\hat{\psi}$ where $\hat{U}_i(\hat{\psi}) \perp\!\!\!\perp R_i | Strata_i$. We use the stratified log-rank test statistic for a device to estimate the

parameter ψ . The stratified log-rank test statistic is obtained from PROC PHREG procedure in SAS. The stratified log-rank test has an asymptotic chi-squared distribution with one degree of freedom under the hypothesis $\psi = \psi_0$ where ψ_0 denotes the true parameter value. From a grid

of values for ψ we choose as $\hat{\psi}$ where the stratified log-rank test statistic has its minimum value. The approximate lower and upper 95% confidence limits are obtained as those values where the stratified log-rank test statistic is close to 3.84. In reality the stratified log-rank test statistic is a step function in ψ and therefore there might be several values where the minimum is obtained and also the upper and lower confidence limits need to be chosen as the point for ψ where the value of the stratified log-rank test statistic changes from less than 3.84 to greater than 3.84.

Complication due to censoring in the estimation algorithm

One complication arises from the fact that due to censoring $U_i(\psi)$ cannot always be computed from the observed data using the above model. One cannot simply replace T_i by X_i in the above model and calculate the respective value, say $U_i^x(\psi)$ from the model because then $U_i^x(\psi)$ would not be independent of R_i and the assumptions for the estimation would not hold. Instead the censoring is handled as follows.

$$C_i(\psi) = \min(C_i, C_i e^\psi)$$

i) If $\delta_i = 1$ then calculate $X_i(\psi) = \min(U_i(\psi), C_i(\psi))$
 $\delta_i(\psi) = I(X_i(\psi) = U_i(\psi))$

$$C_i(\psi) = \min(C_i, C_i e^\psi)$$

ii) If $\delta_i = 0$ then calculate $X_i(\psi) = C_i(\psi)$
 $\delta_i(\psi) = 0$

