By these definitions, $C_i(\psi)$ is independent of $U_i(\psi)$ and R_i . The new censoring time $C_i(\psi)$ can be interpreted as the maximum $U_i(\psi)$ that can be calculated which is smaller than C_i no matter how long individual i is on the randomized active drug. Both $X_i(\psi)$ and $\delta_i(\psi)$ can be calculated based on observed data and furthermore $\{X_i(\psi), \delta_i(\psi)\} \sqcup R_i \mid Strata_i$. Thus the estimation can be performed by calculating $X_i(\psi)$ and $\delta_i(\psi)$ for the various values of ψ within the different strata of the baseline risk factor and proceed as described in the estimation section.

This way of dealing with censoring was introduced by [Robins and Tsiatis 1991](#). Note that some extra censoring will occur due to nature of handling the censoring times in this estimation procedure. This causes some loss of power.

Summary of the method and interpretation

Drug effect is obtained by estimating the multiplicative factor; which would be interpreted as either a relative increase or decrease in survival if one took active drug (Lutathera) compared to taking Octreotide LAR. The multiplicative factor is determined by repeatedly reconstructing the anticipated survival duration of all patients by varying degrees of the factor, until both survival curves (Lutathera arm and Octreotide LAR) can no longer be distinguished, i.e., as if all patients only received Octreotide LAR.

This method maintains the original randomized-group definitions and thus preserves the validity of between group comparison. It provides a randomization based estimate of drug effect corrected for the bias due to crossover (under the assumption that the effect is multiplicative in time). This estimate is valid even in presence of outcome dependent drug change. Of note, this method requires extra censoring (i.e., some events become censored) which impacts the precision of the drug effect estimate.

5.4.3.2 Marginal Structural Cox Proportional Hazards Model using the Inverse Probability of Censoring Weighting (IPCW)

The Marginal Structural Cox Proportional Hazards Model using the Inverse Probability of Censoring Weighting (IPCW) will also be considered ([Hernan et al 2000](#)) to account for the treatment cross-over.

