$$\lambda(t | \bar{A}(t), V) = \lambda_0(t) \exp(\gamma_1 A_i(t) + \gamma_2 V_i); t \leq S_i$$

where a subject stays at risk for death until (s)he switches to the active treatment. Thus, the whole follow-up experience from randomization to $X_i = \min(T_i, C_i)$ is used from subjects randomized to the active treatment arm. But, in the Octreotide LAR arm only the follow-up experience from randomization to $\min(S_i, X_i)$ is used in the marginal structural Cox model. This

means in practice that in the Octreotide LAR arm the data after switching to the open label active treatment is discarded. Each subject is given in this model the case weight indicating the cumulative probability of not switching to the active treatment at time t . Unfortunately, the PROC PHREG procedure does not allow to specify time-dependent weights. Therefore one needs to divide the follow-up time into discrete time intervals and fit the above model using the PROC GENMOD procedure which allows time-dependent weights.

The case weights are estimated using the IPCW scheme for the probability of switching in the Octreotide LAR arm. In the IPCW, the probability of not switching is modeled using two separate logistic regression models as follows:

$$sw_i(k) = \prod_{u=0}^k \frac{\Pr(A_i(u) = a_i(u) \mid \bar{A}_i(u) = (0, \dots, 0)^T, V_i)}{\Pr(A_i(u) = a_i(u) \mid \bar{A}_i(u) = (0, \dots, 0)^T, V_i, \bar{L}_i(u))}$$
$$a_i(u) = \begin{cases} 1 & \text{if subject crossed - over at time } k \\ 0 & \text{if subject did not crossed - over at time } k \end{cases}$$

The first logistic regression model (i.e., the nominator model) uses only the baseline covariate information to describe the probability of switching. The second logistic regression model (i.e., the denominator model) uses both baseline covariate information and time-dependent covariate information. The estimation of these stabilized weights can easily be done with the PROC LOGISTIC procedure in SAS.

Note that the estimation of the stabilized weights is only needed in the Octreotide LAR arm. In the active treatment arm we set the stabilized weights to 1 for all subjects and for all discrete time periods.

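### The Cox interval planned for the RPSFT-adjusted OS hazard ratio treats the estimated psi as known, and no variance method is named for the IPCW fit

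*SAP*

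**What the plan says.** SAP 2.7.1 (Overall Survival) lists three approaches: ITT, RPSFT and IPCW. It says that time to death will be "analysed with three different approaches, that all employ Cox regression to obtain the hazard ratio and its 95% confidence interval". On their status it says "ITT approach is primary. Approaches 2 and 3 are outside the scope of the primary analysis, and will be conducted in the final analysis", and then: "The analysis proceeds by Cox regression as in the primary analysis of PFS". For technical detail on RPSFT and IPCW it points to SAP 5.4.1, but the methods now stand in SAP 5.4.3. SAP 5.4.1 itself has the sentence "Hazard ratio with two-sided 95% confidence interval will be based on Wald test".

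SAP 5.4.3.1 (RPSFT) estimates psi by a grid search on the stratified log-rank statistic after re-censoring. It gives an interval for psi: "The approximate lower and upper 95% confidence limits are obtained as those values where the stratified log-rank test statistic is close to 3.84". It also notes that "this method requires extra censoring (i.e., some events become censored) which impacts the precision of the drug effect estimate". It does not say how the psi limits become limits for a hazard ratio.

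SAP 5.4.3.2 (IPCW) divides follow-up into discrete intervals and says to "fit the above model using the PROC GENMOD procedure which allows time-dependent weights". On the weights it adds: "In the active treatment arm we set the stabilized weights to 1 for all subjects and for all discrete time periods". It names no variance method.

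On standing, SAP 2.7.1 and Protocol 12.5.2 agree that ITT leads and that the adjusted analyses support it. SAP 5.4.3 instead calls ITT supportive, and SAP 5.4.3.1 calls RPSFT the primary OS analysis. Protocol 12.5.2 leaves the details of both adjusted analyses to the SAP.

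**The concern.** In RPSFT the control arm's Lutathera-free survival times are reconstructed with an estimated psi. A Cox model fitted to those times sees them as observed data. Its standard error reflects the number of deaths but not the error in psi, which grows with the share of control patients who cross over.

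The result can contradict the SAP's own output. A valid RPSFT analysis holds no more evidence against the null than the randomized comparison does. The psi interval in SAP 5.4.3.1 respects that; an ordinary Cox interval for the hazard ratio does not.

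Cross-over is built into the design: eligible control patients may receive Lutathera after progression (Protocol 3.3 and 5.2.1), and SAP 5.4.3 warns that the unadjusted comparison is then biased toward no difference. A reader is thus led to the adjusted hazard ratio, whose nominal 95% interval may show a survival benefit that the randomized data do not support.

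**Working it through.** **Design figures.** The documents give no figure for OS or for the adjusted intervals. The PFS figures reproduce. Events = (1.960 + 1.282)² / [(2/9) × (ln 0.5)²] = 98.4, so 99. Critical HR = exp(−1.96/√(99 × 2/9)) = 0.658. Median difference = 15/0.658 − 15 = 7.8 months.

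**What the psi interval tests.** From SAP 5.4.3.1, U(psi) = A·e^psi + (T − A) and C(psi) = min(C, C·e^psi). At psi = 0, U = T and C(psi) = C, so the statistic is the ITT stratified log-rank statistic. Grid steps aside, the psi interval excludes 0 only when the ITT test passes 3.84. Nothing ties the Cox interval for the hazard ratio to that test.

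**RPSFT simulation.** Inputs from the documents: 148 and 74 patients, control median PFS 15 months for the timing of cross-over, accrual 22.2 months, OS follow-up to 48 months after the last randomization, and the SAP's re-censoring rule. Assumed: control median OS of 30 or 45 months and 26–69% of control patients crossing over. The analysis was unstratified, with 600 trials per scenario. Psi was found by grid search, then Cox was fitted to observed Lutathera times against counterfactual control times. Exposure was coded as time on Lutathera, which matches the interpretation of e^psi in SAP 5.4.3.1 but not its literal definition of A.

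Results with no true effect:

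| Median OS (months) | Crossing over | Cox SE | True SD of log HR | Coverage | Cox CI below 1 | ITT in favour | Cox CI below 1, ITT not |
|---|---|---|---|---|---|---|---|
| 30 | 26% | 0.169 | 0.223 | 87.2% | 6.7% | 2.5% | 4.2% |
| 30 | 39% | 0.169 | 0.259 | 82.2% | 8.7% | 2.5% | 6.2% |
| 30 | 52% | 0.170 | 0.305 | 74.0% | 12.3% | 2.5% | 9.8% |
| 30 | 62% | 0.171 | 0.353 | 68.0% | 15.2% | 2.5% | 12.7% |
| 45 | 29% | 0.189 | 0.259 | 85.7% | 7.0% | 3.8% | 4.0% |
| 45 | 44% | 0.190 | 0.300 | 80.8% | 9.5% | 3.8% | 6.3% |
| 45 | 58% | 0.191 | 0.359 | 72.8% | 14.3% | 3.8% | 11.2% |
| 45 | 69% | 0.193 | 0.414 | 66.3% | 17.0% | 3.8% | 13.7% |

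The Cox interval therefore has between 0.169/0.223 = 76% and 0.193/0.414 = 47% of its proper width. With a true ratio of 0.8, coverage is 70–87%, and in 9–26% of trials the adjusted interval lies below 1 while ITT is not significant. The log-rank-inversion interval for psi covers 93–96% throughout.

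A second set of runs assumed a control median OS of 36 months. Coverage was 87–89% with 50% switching and 75–76% with 80%. False benefit was 6.5% and 12.7%, against 2.5–2.8% for ITT. The mean HR estimate was 0.67 for a true 0.667, so the fault lies in the interval and not in the estimate.

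**One trial, assumed numbers.** Adjusted HR 0.67 (log −0.400), Cox SE 0.17, ITT z = −1.2.
- Cox interval: exp(−0.400 ± 1.96 × 0.17) = 0.48 to 0.93.
- Test-preserving interval: SE = 0.400/1.2 = 0.334, so exp(−0.400 ± 1.96 × 0.334) = 0.35 to 1.29.

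**IPCW simulation.** Stabilized weights, pooled logistic regression on 3-month intervals, 500 trials per scenario. The assumed switch probabilities at progression (good/poor Karnofsky) set the scenarios. The estimator was itself off-centre under the assumed confounding, so coverage is measured around its own mean; this isolates the variance.

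| Switching | Naive coverage | Patient-clustered robust coverage |
|---|---|---|
| 0.5/0.3 | 94–96% | 95–97% |
| 0.8/0.4 | 88–90% | 94–96% |
| 0.9/0.6 | 79–82% | 91–93% |

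**The case against.** The strongest reply is that the SAP already has a valid RPSFT interval. SAP 5.4.3.1 inverts the log-rank test, presents the multiplicative factor as the drug effect, and admits the loss of precision. That stands: the gap is confined to the hazard-ratio scale. But SAP 2.7.1 asks for that hazard ratio and its interval by Cox regression, so the gap is real.

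Next, the Wald interval is an inference. The Wald sentence sits in a section written for PFS, 2.7.1 reaches it through a cross-reference that no longer fits, and the sentence on proceeding as for PFS may mean ITT only. SAP 5.4.3.1 also never spells out a Cox fit to counterfactual times. All of that is fair as to the exact form. It does not rescue the plan: the sentence in 2.7.1 covers all three approaches by name, and any ordinary Cox interval on adjusted times takes psi as fixed.

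For IPCW the SAP is silent on variance, so a naive interval is only one reading. Splitting follow-up into rows does no harm by itself, because a discrete-time likelihood factorises over a patient's intervals; the weighting is what upsets the naive variance. A reader might infer that both adjusted intervals are far too narrow whatever the switching. The IPCW results do not support that: the naive interval is near nominal at low switching. Nor is treating the weights as known the main cause, since a robust variance that still does so largely restores coverage.

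Last, OS lies outside the testing hierarchy (SAP 5.4.1) and carries no alpha. A reader might infer that the trial's type I error is inflated; it is not.

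**Conclusion.** The point holds for RPSFT. Following SAP 2.7.1 gives an adjusted hazard ratio whose 95% interval omits the error in psi and can disagree with both the ITT test and the psi interval of SAP 5.4.3.1. Over both sets of runs, coverage is about 66–89% and false benefit under no effect about 6.5–17%, against 2.5–3.8% for ITT. These ranges rest on assumed OS medians and cross-over rates and are not properties of this trial; the direction, and the worsening with more cross-over, hold throughout.

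For IPCW the defect is an unstated variance method, which matters at moderate to heavy switching.

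The consequence is misinterpretation of supportive analyses at the final analysis. It becomes more serious if SAP 5.4.3.1, which makes RPSFT primary, is followed in place of 2.7.1. The change should be made before the final analysis.

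**What to change.** In SAP 2.7.1 and 5.4.3:

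- **RPSFT.** Obtain the hazard-ratio interval by bootstrapping patients within arm and stratum and repeating the whole procedure each time (psi search, re-censoring, Cox). Alternatively use the test-based interval with SE = |log HR| / |ITT z|, which keeps the ITT p-value. The bootstrap is safer when the ITT z is close to zero, where that ratio is unstable. Report the psi interval beside it.
- **IPCW.** Specify a patient-clustered robust variance, or a patient-level bootstrap that refits the weight models.
- **Consistency.** Point 2.7.1 to 5.4.3 in place of 5.4.1. Reconcile 2.7.1 (ITT primary) with 5.4.3 and 5.4.3.1 (ITT supportive, RPSFT primary).

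The cost is SAP wording and computing time, and the reported intervals will be wider. No data collection changes, and the primary PFS analysis is untouched.

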2.7.2 Statistical hypothesis, model, and method of analysis

DCR: DCR per either central or local assessment will be summarized using descriptive statistics (N, %) by treatment group along with two-sided exact binomial 95% CIs.

DOR: DOR will be listed and summarized for patients with BOR of CR or PR (unconfirmed). The distribution of duration of response will be estimated using the Kaplan-Meier method and the median duration of response will be presented along with 95% confidence interval. In addition, a swimmer plot will show the time to onset and duration of response based on central review for all patients with unconfirmed CR or unconfirmed PR.

PFS2: PFS2 analyses will be based on the FAS population according to the randomized treatment group and strata assigned at randomization. The PFS2 distribution will be estimated using the Kaplan-Meier method, and Kaplan-Meier curves, median and associated 95% confidence intervals will be presented for each treatment group.

For the efficacy analysis in the re-treatment phase, all efficacy analysis (ORR, DOR, DCR, PFS, PFS2, OS) will be descriptive in nature only.

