12.5.2 Other efficacy endpoints

Disease Control Rate (DCR) is defined as rate of patients with best overall response of partial response (PR), complete response (CR), or stable disease (SD) (centrally assessed according to RECIST 1.1). More precisely, it counts the presence of at least one confirmed CR or confirmed PR or SD. The DCR will be calculated based on FAS according to the ITT principle. DCR and its 95% confidence interval will be presented by treatment group. The Cochrane-Mantel-Haenszel chi-square test, stratified by the randomization stratification factors, will be used to compare DCR between the two treatment groups, at the one-sided 2.5% level of significance. The p-value to be generated using the Cochrane-Mantel-Haenszel chi-square test is considered nominal, and not to be considered confirmatory as it is not part of the testing strategy. The SAP will advise on how to proceed in case of few events in any stratum.

Duration of response (DOR) only applies to subjects whose best overall response is complete response (CR) or partial response (PR) according to RECIST 1.1 based on tumor response data per local review. The start date is the date of first documented response of CR or PR (i.e., the start date of response, not the date when response was confirmed), and the end date is defined as the date of the first documented progression per local review or death due to underlying cancer. Subjects continuing without progression or death due to underlying cancer will be censored at the date of their last adequate tumor assessment. DOR will be listed and summarized by treatment group for all subjects in the FAS with confirmed BOR of CR or PR.

OS is defined as the time from date of randomization to date of death due to any cause. If a subject is not known to have died, then OS will be censored at the latest date the subject was known to be alive (on or before the cut-off date).

OS will be analyzed in the FAS population according to the randomized treatment group and strata assigned at randomization. At the time of the PFS primary analysis, the OS distribution will be estimated using the Kaplan-Meier method, and the Kaplan-Meier curves, medians and

95% confidence intervals of the medians will be presented for each treatment group. The hazard ratio for OS will be calculated, along with its 95% confidence interval, using a stratified Cox model.

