12.6 Analysis of exploratory endpoints

12.6.1 PFS2

PFS2 is defined as time from date of randomization to the first documented local progression on next-line therapy or death from any cause, whichever occurs first. The first documented progression on next-line treatment is based on investigator assessment of PD (i.e. as captured on the anti-neoplastic therapy after treatment discontinuation eCRF page); it is not necessary to continue to collect tumor assessments data for subsequent anti-neoplastic therapies for the purpose of PFS2.

- Next-line therapy is defined as the first new (systemic) anti-neoplastic therapy initiated after discontinuation of study treatment regardless of EoT reason. Drugs given as part of the same regimen should be considered as first line (i.e. part of the next-line therapy).
- New anti-neoplastic therapies after EoT will be collected in the anti-neoplastic therapy after treatment discontinuation eCRF page including start/end date, reason for discontinuation, date and type of progression («clinical» vs «radiologic»).
- PFS2 will be censored if no PFS2 event (progression or death) is observed during next-line therapy before the analysis cut-off date; the censoring date will be the last contact date.
- However, in case a second new anti-neoplastic therapy is introduced without prior PFS2 event, then PFS2 will be censored at the end date of the first new anti-neoplastic therapy (i.e. next line therapy).
- Any death prior to initiation of next-line therapy will be considered as an event for PFS2. Any death occurring following end of next line therapy will be considered as an event if no second new anti-neoplastic therapy has been introduced.

• PFS and PFS2 may be identical if a subject did not experience an event (i.e. progression) prior to initiation of next-line therapy, and adequate tumor assessments continue until RECIST 1.1-documented disease progression after initiation of next-line therapy.

PFS2 will be analyzed in the FAS population according to the randomized treatment group and strata assigned at randomization. The PFS2 distribution will be estimated using the Kaplan-Meier method, and the Kaplan-Meier curves, medians and 95% confidence intervals of the medians will be presented for each treatment group. The hazard ratio for PFS2 will be calculated, along with its 95% confidence interval, using a stratified Cox model.

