2.7 Analysis of other secondary and exploratory objective(s)

Other secondary objectives of the study are to compare the two treatment groups with respect to:

1. DCR: Disease Control Rate, the proportion of patients with a best overall response of CR, PR, or SD per central review. Timing: at the primary analysis of PFS.
2. DOR: Duration of Response per central review, time from first complete or partial response to progression or death due to underlying cancer. Timing: at the primary analysis of PFS.
3. OS: time from the randomization date until the day of death due to any cause. Timing of final analysis: when all patients have either had an event, are lost to follow-up, or, four years have elapsed from the randomization of the last patient or six months after the last cross-over or re-treatment dose in the study, whichever occurs last.
4. Rate of adverse events and laboratory toxicities (scored according to CTCAE grade). See [Section 2.8](#) for safety analyses.

Further, these exploratory endpoints are also covered in this section:

- Time to second progression (PFS2), the time from randomization to objective tumor progression on next line treatment or death due to any cause, assessed locally according to RECIST 1.1
- Health related quality of life (QoL) scales, TTD for items/scales not included among key secondary endpoints as well as change from baseline in the total score for health status from the EQ-5D questionnaire.

- PK of octreotide long-acting at the high dose of 60 mg by examining the steady-state trough plasma concentration of octreotide.

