3.1 Power for analysis of key secondary variables

No power calculation has been performed for the key secondary variables.

4 Change to protocol specified analyses

Not applicable

5 Appendix

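### SAP 2.7.2 omits two between-arm analyses that the protocol specifies, the stratified CMH comparison for DCR and the stratified Cox hazard ratio for PFS2, and SAP Section 4 declares no change

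*SAP*

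**What the plan says.** **Protocol, DCR (12.5.2).** Arms are compared by the CMH method, in these words: "stratified by the randomization stratification factors, will be used to compare DCR between the two treatment groups, at the one-sided 2.5% level of significance". That p-value carries limited weight: it "is considered nominal, and not to be considered confirmatory as it is not part of the testing strategy". One detail is left open: "The SAP will advise on how to proceed in case of few events in any stratum".

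**Protocol, PFS2 (12.6.1).** Kaplan-Meier curves and medians by arm, and a between-arm estimate: "The hazard ratio for PFS2 will be calculated, along with its 95% confidence interval, using a stratified Cox".

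**SAP, objective (2.7).** "Other secondary objectives of the study are to compare the two treatment groups with respect to" a four-item list that DCR heads. PFS2 stands in a separate exploratory list below it.

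**SAP, method (2.7.2).** "DCR per either central or local assessment will be summarized using descriptive statistics (N, %) by treatment group along with two-sided exact binomial 95% CIs". For PFS2, the text names the full analysis set and the randomization strata, then gives Kaplan-Meier curves, medians and their confidence intervals for each arm, and stops there.

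**SAP, declared changes (Section 4).** Under the heading "Change to protocol specified analyses" the entry is that none applies. SAP Section 1 says the SAP rests on protocol version 2.0, the version that contains both analyses.

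**The concern.** A SAP may add detail to a protocol analysis or replace it, but a replacement should be visible and reasoned. Here a statistician who follows the SAP to the letter would produce neither the DCR comparison nor the PFS2 hazard ratio, and the document would not show that the plan had changed. In an open-label trial, an unexplained omission invites questions later about when and why it was made.

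The content matters too. For DCR, the SAP's stated aim of comparing the arms is left with two separate proportions, without the stratification used at randomization. For PFS2, medians and curves give no summary of the treatment effect with its uncertainty, so the aim of exploring the effect of Lutathera has no estimate attached.

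**Working it through.** **1. The plan's own design figure, and whether this point touches it.** Inputs from SAP Section 3 (same in protocol 12.8.1): hazard ratio 0.50, one-sided 2.5%, 90% power, 2:1 allocation.

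- Events = (1.960 + 1.282)² / [(2/3)(1/3)(ln 0.5)²] = 98.4, rounded up to 99. Reproduced.
- Critical hazard ratio = exp(−1.96 / √(99 × 2/9)) = 0.658, and 15/0.658 − 15 = 7.8 months. Reproduced.

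These concern PFS only. The documents state no power or precision for DCR or PFS2, so no stated figure is wrong and none changes.

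**2. Protocol and SAP side by side.**

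| | Protocol | SAP |
|---|---|---|
| DCR, between arms | Stratified CMH test, nominal p-value (12.5.2) | None (2.7.1, 2.7.2) |
| DCR, sparse strata | Left to the SAP (12.5.2) | No rule for DCR |
| DCR, aim | Evaluate against the comparator (Table 2-1) | Compare the two groups (2.7) |
| PFS2, between arms | Stratified Cox hazard ratio, 95% CI (12.6.1) | None (2.7.1, 2.7.2) |
| PFS2, timing | Not tied to one analysis (12.6.1) | Final analysis only (2.7.1) |
| Declared change | – | None (Section 4) |

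**3. Whether another part of the SAP supplies them.** Appendix 5.4.1 describes the log-rank and Cox methods for PFS. Appendix 5.4.2 describes the CMH method for ORR. SAP 2.7.1 defines DCR and PFS2 and sets the PFS2 event and censoring rules, but gives no between-arm method. The SAP's revision history names other removals, such as supplementary ORR analyses. For PFS2 it mentions only updated rules and a clarified plan, and for DCR only the progression window. It records neither removal.

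**4. Whether the SAP makes these endpoints descriptive on purpose.** SAP 2.7.2 restricts efficacy to description only for the re-treatment phase. SAP 2.7.1 rules out a between-group comparison only for DOR, in line with protocol 8.3.2. Neither statement covers DCR or PFS2 in the randomized comparison.

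**5. What per-arm output leaves out (illustration only).** The counts are assumed, because the documents give no expected DCR. The arm sizes of 148 and 74 are the planned ones, and the calculation is unstratified.

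- Lutathera 130/148 = 87.8%, exact 95% CI 81.5 to 92.6. Control 56/74 = 75.7%, CI 64.3 to 84.9. The intervals overlap.
- Difference = 87.8 − 75.7 = 12.2 points (from unrounded values). Standard error = √(0.878 × 0.122/148 + 0.757 × 0.243/74) = 0.0567. The 95% CI is 1.1 to 23.3 points.
- Test: pooled proportion 186/222 = 0.838; z = 0.1216 / √(0.838 × 0.162 × (1/148 + 1/74)) = 2.32; one-sided nominal p = 0.010.

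So two per-arm intervals can look inconclusive when the direct comparison is not. For PFS2, a hazard ratio CI runs from the estimate divided by, to the estimate multiplied by, exp(1.96 / √(d × 2/9)). With d assumed at 60, 99 or 150 events the factor is 1.71, 1.52 or 1.40. The SAP as written reports no such interval.

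**The case against.** The strongest reply is that little depends on either analysis. The protocol itself puts the DCR p-value outside the testing strategy. PFS2 is exploratory, and protocol 8.3.2 and 12.6.1 and SAP 2.7.1 all warn that cross-over and sparse scans limit what it can show. This stands, and it limits the weight of the point. It does not explain the omission: the protocol gave the same cautions and still specified both analyses, and the SAP keeps a Cox hazard ratio for overall survival, which is also affected by cross-over.

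A second reply is that comparing need not mean testing here, since the same SAP list includes DOR and adverse event rates, which are reported descriptively. For DCR, however, the protocol says what the comparison is: the CMH test "will be used to compare DCR between the two treatment groups".

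Three stronger readings are tempting, and the documents do not support them.

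- *The DCR objective cannot be answered.* A crude difference can be computed from the reported counts, as in the illustration. What cannot be rebuilt from arm totals is the stratified comparison.
- *The trial loses power for DCR.* Judging by non-overlap of the two exact intervals, instead of by an unstratified test, would lower power from 82% to 47% at assumed DCRs of 90% versus 75%. But neither document proposes that rule, the rates are assumptions, and no decision rests on a nominal p-value.
- *The SAP abandons a stated comparison for PFS2.* The sentence about comparing the groups heads the list with DCR. The PFS2 aim is to explore an effect. The SAP also names the strata for PFS2, so the missing hazard ratio may be an unfinished paragraph rather than a decision.

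**Conclusion.** The point holds as a discrepancy between protocol and SAP with a modest analytic consequence. Two between-arm analyses in protocol version 2.0 are absent from the SAP, and the Section 4 entry is therefore incorrect. For DCR, the SAP's own aim lacks a stratified between-arm estimate or test, and the sparse-strata rule that the protocol expected from the SAP is also missing. For PFS2, no between-arm effect estimate remains.

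Type I error, the primary analysis, the key secondary hierarchy, the sample size and the event trigger are unaffected. The conclusion rests on the text alone; the DCR counts and PFS2 event numbers above are assumptions used for illustration. Whether the omission was deliberate cannot be told from the documents.

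**What to change.** In SAP 2.7.2:

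- **DCR:** restore the CMH comparison stratified by the randomization factors, reporting the odds ratio, its 95% CI and a p-value labelled nominal. Add the sparse-strata rule. SAP 5.4.2 already has one for ORR (the Mantel-Fleiss check, with an exact test if it fails), which could be extended to DCR by reference.
- **PFS2:** restore the stratified Cox hazard ratio with 95% CI, at the final analysis where the SAP already places PFS2, and keep the existing caution about cross-over and scan frequency.

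If the removal is intended, list both omissions in SAP Section 4 with the reason, and reword the DCR objective in SAP 2.7 so that it no longer promises a comparison.

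The cost is SAP wording and a small amount of added output. The data, the strata and the methods are already specified for ORR and PFS. Alpha, sample size and event count do not change.
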